Ibrutinib 420 mg will be dosed orally (PO), once daily (QD) starting on Day –1. Venetoclax will be initiated on Week 1, Day 1 with an initial 5-day dose ramp-up for venetoclax ([Figure 1](#)). Venetoclax 400 mg (target dose) will be dosed PO, QD; an option to increase the dose of venetoclax to 600 mg QD will be available at Week 8 or thereafter if there is evidence of incomplete response and/or if the dose of ibrutinib has been decreased to 280 mg/day or 140 mg/day due to toxicity management. The dose of venetoclax should not be increased to 600 mg/day in subjects with significant venetoclax toxicity. The maximum dose allowed for venetoclax is 600 mg/day.

Treatment duration of combination treatment will be as follows:

- eligible subjects will proceed to stem cell transplantation after reaching CR (combination therapy will be discontinued but subjects will be followed for disease progression)
- up to 2 years, will be given to subjects who are ineligible for stem cell transplantation unless treatment is intolerable or the subject develops progressive disease

[figure not shown]
For subjects who continue to derive clinical benefit after 2 years of treatment, AbbVie will work with the investigator to consider the potential continuation of therapy, as per local regulations.

See Section 5 for information regarding eligibility criteria.

The dosing schematic is shown in Figure 1. To mitigate the risk of tumor lysis syndrome (TLS) (see Section 6.2) with venetoclax, a 5-step dose ramp-up with hospitalization for close monitoring and prophylaxis has been developed. Due to the aggressive nature of T-PLL, the venetoclax ramp-up will be administered in a daily manner, starting with 20 mg on Week 1, Day 1 and reaching the target dose of 400 mg on Week 1, Day 5. Refer to Section 6.2 for details for TLS management.

Further information regarding study procedures is located in the Operations Manual Section 3.

Figure 1. Dosing Schematic

CR = complete remission; D = day; W = week

Note: Venetoclax 5-step dose ramp-up in 5 days to target dose of 400 mg daily with an option to increase the dose to 600 mg QD at Week 8 or thereafter if there is evidence of incomplete response and/or if the dose of ibrutinib has been decreased to 280 mg/day or 140 mg/day due to toxicity management.

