Congenital Anomaly	An anomaly detected at or after birth, or any anomaly that results in fetal loss.
Persistent or Significant Disability/Incapacity	An event that results in a condition that substantially interferes with the activities of daily living of a study subject. Disability is not intended to include experiences of relatively minor medical significance such as headache, nausea, vomiting, diarrhea, influenza, and accidental trauma (e.g., sprained ankle).
Important Medical Event Requiring Medical or Surgical Intervention to Prevent Serious Outcome	An important medical event that may not be immediately life-threatening or result in death or hospitalization, but based on medical judgment may jeopardize the subject and may require medical or surgical intervention to prevent any of the outcomes listed above (i.e., death of subject, life-threatening, hospitalization, prolongation of hospitalization, congenital anomaly, or persistent or significant disability/incapacity). Additionally, any elective or spontaneous abortion or stillbirth is considered an important medical event. Examples of such events include allergic bronchospasm requiring intensive treatment in an emergency room or at home, blood dyscrasias or convulsions that do not result in inpatient hospitalization, or the development of drug dependency or drug abuse.

All AEs reported from the time of study drug administration until 30 days after discontinuation of study drug administration will be collected, whether solicited or spontaneously reported by the subject. In addition, protocol-related SAEs and protocol-related nonserious AEs will be collected from the time the subject signs the study-specific informed consent.

The following definitions will be used for a Serious Adverse Reaction (SAR) and Suspected Unexpected Serious Adverse Reaction (SUSAR):

SAR	Defined as all noxious and unintended responses to an Investigational Medicinal Product (IMP) related to any dose administered that result in an SAE as defined above.
SUSAR	A suspected SAR: refers to individual SAE case reports from clinical trials where a causal relationship between the SAE and the IMP was suspected by either the sponsor or the investigator, is not listed in the applicable Reference Safety Information, and meets one of the above serious criteria. All individually reported SARs are considered suspected.

AbbVie will be responsible for SUSAR reporting for the IMP in accordance with global and local requirements.

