2.2 Individual Post-Treatment Period Visit Activities

This section presents a list of activities performed during each visit, organized by visit. The dot pattern on the upper right indicates the place of the visit in the overall post-treatment period activity schedule.

Activities are grouped by category (interview, examination, etc.). Further information about the activities is presented in Section 3.

30-Day Follow-Up Visit:

 INTERVIEW	Adverse event assessment	Concomitant therapy
 EXAMINATION	Physical examination Weight	Vital signs
 LABORATORY	Hematology/chemistry sample	Urine pregnancy test

NOTES: Follow-up visit to be conducted no earlier than 30 days after the last dose of study drug (venetoclax or ibrutinib) but prior to any new anticancer therapy. A symptom-directed physical examination will be performed at the follow-up visit. Urine pregnancy testing to be performed every 4 weeks up to 30 days after the last dose of venetoclax and 90 days after the last dose of ibrutinib, whichever the latest.

Post-Treatment Follow-Up Visits:

 INTERVIEW	Adverse event assessment	Concomitant therapy
 EXAMINATION	Physical examination Weight Physical examination (or ultrasound) of lymph nodes and spleen	Vital signs Clinical response assessment
 LABORATORY	Hematology/chemistry sample Computed tomography (if needed for confirmation of CR/CRi)	Bone marrow sample (if needed for confirmation of CR/CRi) Blood sample for optional biomarker assessments

NOTES: Post-treatment follow-up visits will be conducted until documented progressive disease (PD) or other post-treatment therapies (including stem cell transplantation) are received. The post-treatment follow-up visits will follow the same schedule as the visit schedule (i.e., Week 4, Week 8, Week 12, Week 16, Week 24, Week 36, and every 12 weeks thereafter).

Clinical response assessment is based on physical examination (or ultrasound) and blood sample.

Spleen and lymph node measurements will be performed during the physical examination or via ultrasound.

If clinical response assessment is suggestive of a CR/CRi, a CT will be taken for confirmation of the clinical response. If a CT scan indicates a CR/CRi, a bone marrow biopsy will be required as soon as possible to confirm the clinical response (the sample will be split for analyses of disease and biomarker assessments).

Blood samples will be collected for optional biomarker assessments for subjects who provided consent for the correlative studies.

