4.2 Recording Data and Analyses of Safety Findings

AEs will be coded using the Medical Dictionary for Regulatory Activities (MedDRA). The number and percentage of subjects with treatment-emergent AEs (i.e., any event that begins or worsens in severity after initiation of study drug through 30 days poststudy drug dosing) will be tabulated by primary MedDRA system organ class (SOC) and preferred term. The tabulation of the number of subjects with treatment-emergent AEs by severity grade and relationship to study drug also will be provided. Subjects reporting more than 1 AE for a given MedDRA preferred term will be counted only once for that term using the most severe grade according to the severity grade table and the most related according to the relationship to study drug tables. Subjects reporting more than 1 type of event within an SOC will be counted only once for that SOC.

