7.2 Analysis of Adverse Events

All summaries/analyses involving AEs will include treatment-emergent adverse events (TEAE) only, unless otherwise specified. TEAE are defined as any event with onset after the first dose of study drug and no more than 30 days after the last dose of study drug. Events where the onset date is the same as the study drug start date are assumed to be treatment-emergent, unless the study drug start time and the AE start time are collected and the AE start time is prior to the study drug start time. If an incomplete onset date was collected for an AE, the AE will be assumed to be treatment-emergent unless there is evidence that confirms that the AE was not treatment-emergent (e.g., the AE end date was prior to the date of the first dose of study drug).

For summaries of AEs related (reasonable possibility) to study drug, at each level of summation (overall, SOC, and PT) each subject is counted only once. If a subject has an AE with unknown relationship, then the subject will be counted in the relationship category of "unknown," even if the subject has another occurrence of the same event with a relationship of "no reasonable possibility" present. The only exception is if the subject has another occurrence of the same AE with the relationship of "reasonable possibility." In this case, the subject will be counted under the reasonable possibility category.

Adverse event data will be summarized and presented using primary MedDRA system organ classes (SOCs) and preferred terms (PTs) according to the MedDRA coding dictionary version 21.0 or higher.

The number and percentage of subjects experiencing treatment-emergent adverse events will be summarized for the following adverse event summaries:

- Any treatment-emergent adverse event.
- Any treatment-emergent adverse event with NCI toxicity (CTCAE version 5.0) grade 3, 4, or 5 adverse events.
- Any treatment-emergent adverse event with NCI toxicity (CTCAE version 5.0) grade 3 or 4 adverse event.
- Adverse events broken down by NCI toxicity grade (Severity).
- Any treatment-emergent serious adverse event.
- Any treatment-emergent adverse event leading to discontinuation of venetoclax.
- Any treatment-emergent adverse event leading to venetoclax interruption.
- Any treatment-emergent adverse event leading to venetoclax reduction.
- Any treatment-emergent adverse event that is rated at least possibly related to venetoclax by the investigator (Reasonable Possibility Related)

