For shifts relative to National Cancer Institute Common Toxicity Criteria for Adverse Events (NCI CTCAE version 5.0), baseline and post-baseline laboratory observations (maximum and final) will be categorized as grade 0, grade 1, grade 2, grade 3, or grade 4 according to NCI CTCAE grade version 5.0. For laboratory tests for which a normal range limit is one end of the grade 1 range then values that are either within the normal range or outside it in opposite direction will be classified as grade 0 values.

The baseline and final grades will be defined respectively as the grade of the last measurement collected prior to the first dose of study drug unless specified differently, and as the last post-baseline measurement collected no more than 30 days after the last dose of study drug. The maximum NCI toxicity grade value is the value with highest NCI toxicity grade collected after the first dose of study drug and within 30 days following the last dose of study drug. In cases where multiple values are collected on the same day, the maximum grade value will be selected as the value for that day.

For each variable, shift tables will be generated that cross tabulate the number of subjects with baseline values of grade 0, grade 1, grade 2, grade 3, or grade 4 versus maximum or final observations of grade 0, grade 1, grade 2, grade 3, or grade 4.

Detailed listings of data for subjects experiencing NCI CTCAE grade 3 to 4 blood chemistry and hematology values will be provided. All measurements collected, regardless of the number of days after the last dose of study drug, will be included in these listings.

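### The 30-day windows for adverse events and worst laboratory grade do not close when conditioning, transplant or new therapy starts, so toxicity of later treatment can enter the all-cause safety tables

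*SAP*

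**What the plan says.** SAP 7.2 defines a treatment-emergent event by timing alone: "onset after the first dose of study drug and no more than 30 days after the last dose of study drug". Operations Manual 4.2 uses the same 30 days and also counts worsening: "any event that begins or worsens in severity after initiation of study drug through 30 days poststudy drug dosing". Protocol 6.1 sets collection to match: "All AEs reported from the time of study drug administration until 30 days after discontinuation of study drug administration will be collected". For laboratory shifts, SAP 7.3 says "The maximum NCI toxicity grade value is the value with highest NCI toxicity grade collected after the first dose of study drug", again up to 30 days after the last dose.

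Transplant is a planned exit from treatment. Protocol 4.1 states that "eligible subjects will proceed to stem cell transplantation after reaching CR (combination therapy will be discontinued but subjects will be followed for disease progression"). The Operations Manual (2.2, 30-Day Follow-Up Visit) places the safety visit "no earlier than 30 days after the last dose of study drug (venetoclax or ibrutinib) but prior to any new anticancer therapy". Operations Manual 3.19 adds that procedures at discontinuation should not hold up new treatment.

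No section closes the safety window, or flags events, at conditioning, transplant or new therapy.

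**The concern.** Safety and tolerability is a secondary objective of a single-arm study, so no comparator would absorb toxicity that belongs to the next treatment. One route to that next treatment is set by the plan itself: a complete responder who is eligible for transplant stops both drugs and goes on to it. If conditioning begins inside the 30 days, its cytopenias, infections or deaths meet the definition of treatment-emergent. Neutropenia is an event of special interest in Protocol 6.1, and SAP Table 2 also selects serious infection, anemia, thrombocytopenia and hemorrhage, so these summaries are exposed.

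The SAP already separates later therapy for efficacy. In SAP 6.3, PFS and TTP are censored before non-protocol therapy and EFS has a transplant censoring date. SAP 6.4 offers a sensitivity analysis that censors before transplant. The safety sections have no counterpart.

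**Working it through.** **Which tables are open to the effect**

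| Output | Limited by attribution? | Could later-treatment toxicity enter? |
|---|---|---|
| Any event, Grade 3 to 5, serious, fatal (SAP 7.2) | No | Yes, if onset is within 30 days of last dose |
| Selected events (SAP Table 2) | No | Yes, same condition |
| Related to venetoclax; related to ibrutinib (SAP 7.2) | Yes, by investigator | Only if rated a reasonable possibility; Protocol 6.1 has the investigator weigh alternative causes |
| Maximum-grade laboratory shifts (SAP 7.3) | No | Only if values are recorded; Operations Manual 2.2 and 3.11 end scheduled post-treatment visits once transplant or other therapy is received |

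**Can later treatment start inside the window?** The visit rule in Operations Manual 2.2 presumes that it starts after day 30. Operations Manual 3.19 leaves an earlier start possible. If it does start earlier, the two conditions on the visit (day 30 or later, and before new therapy) cannot both be met, and no section says how to count the events.

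**Size.** The plan gives no figure on this point to reproduce. The denominators come from the two-stage design table (Protocol Table 6, SAP Table 1): 31, 34 or 37 relapsed or refractory subjects if Stage 2 opens. As a check on that table, exact binomial calculation, rejecting when total responses exceed r(S), gives a type I error of 0.0496 at 20% and power of 0.8003 at 40%, against the stated 0.05 and 80%.

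Let q be the proportion with the event on study drug, and k the number with a later-treatment event of that type inside the window. If the k subjects are as likely as the others to have had the event already:

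observed proportion = q + (k/N)(1 − q), so the addition is (k/N)(1 − q), with ceiling k/N.

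Both k and q are assumptions. Additions in percentage points, N = 37 to N = 31:

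| k | q = 0 (ceiling) | q = 30% | q = 60% |
|---|---|---|---|
| 0 | 0 | 0 | 0 |
| 1 | 2.7 to 3.2 | 1.9 to 2.3 | 1.1 to 1.3 |
| 3 | 8.1 to 9.7 | 5.7 to 6.8 | 3.2 to 3.9 |
| 5 | 13.5 to 16.1 | 9.5 to 11.3 | 5.4 to 6.5 |

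For example, with k = 3 and q = 30%, the rate becomes 0.30 + (3/37)(0.70) = 35.7% at N = 37 and 0.30 + (3/31)(0.70) = 36.8% at N = 31.

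**The case against.** The strongest reply is that the plan is consistent and that the overlap may never occur. Protocol 6.1, Operations Manual 4.1 and 4.2 and SAP 7.2 all use 30 days, and a subject managed to the visit schedule starts new therapy after the window has closed. That stands as far as it goes: nothing in the documents says how often, or whether, later treatment starts earlier. But the visit rule times a visit and does not restrict the analysis.

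Second, treatment-emergent is a category of timing, not of cause. This also stands. A reader might infer that conditioning toxicity will be reported as toxicity of venetoclax plus ibrutinib. The documents do not support that, because drug-related events are tabulated separately on the investigator's attribution.

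Third, the laboratory route is weak, since scheduled visits stop at transplant or other therapy. In addition, Protocol 6.1 makes a laboratory abnormality an adverse event only under stated conditions, so a Grade 4 cytopenia does not enter the event tables automatically. Both points stand, and they narrow the concern mainly to clinical events and unscheduled values.

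Fourth, truncating the main table would remove possible late effects of the study drugs. That is a good reason to keep the 30-day table. It does not count against adding a second one.

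Finally, SAP 3.0 leaves analysis conventions to a programming plan that is not among the documents and might deal with this. The treatment-emergent window is defined in the SAP, so a supplementary version of it is better prespecified there too.

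**Conclusion.** The gap is real and modest. Both safety windows run a fixed 30 days whatever treatment follows, and the all-cause, Grade 3 to 5, serious, fatal and selected-event tables have no filter that would keep out toxicity of later treatment. The laboratory shifts are affected only through values recorded after later treatment starts.

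The size cannot be stated from the documents. Each affected subject adds at most 2.7 to 3.2 points to a term, less where the event had already occurred on study drug, and the effect is zero if no one starts later treatment within 30 days. The rows for three and five subjects are illustrations, not forecasts.

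A reader might go further and infer that the better the regimen works as a bridge to transplant, the worse its safety will look. That would need a known, short interval from last dose to conditioning, and the documents give none. Subjects who move to other therapy after progression would also contribute, and for them the link with good response does not hold. The primary endpoint is untouched. This is an inexpensive improvement to an uncontrolled secondary objective, not a flaw that undermines the trial.

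**What to change.** Keep the 30-day tables as the main safety analysis. In SAP 7.2 and 7.3, prespecify a supplementary summary of treatment-emergent events and maximum laboratory grades, truncated at the earlier of 30 days after last dose and the day before conditioning, transplant or new anti-T-PLL therapy. Flag events after that point but still within 30 days in a listing, so that no safety information is lost.

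Operations Manual 3.11 already collects dates of post-study anticancer treatment, including transplant. It does not name the start of conditioning, so record that date if it is not captured among them.

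Reconcile the 30-day visit rule in Operations Manual 2.2, the discontinuation text in Operations Manual 3.19 and the window in SAP 7.2 on whether new therapy can start inside the 30 days.

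The cost is a short SAP amendment, one extra set of tables and a listing, and possibly one added date field. Prespecifying the summary also avoids choosing a cut-off after the results are known.
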